Two-sided 95% confidence intervals will be provided for primary and secondary endpoints defined by proportions. Confidence intervals will also be calculated for differences between pre-defined groups of patients, if appropriate (e.g. LCIG as monotherapy vs. LCIG plus add-on therapy).

Logistic regression and subgroup analyses will be applied to investigate the impact of potential prognostic factors for LCIG monotherapy. Potential prognostic factors used for the regression model will include demographic variables (ie. age, gender, race) and baseline disease characteristics at LCIG initiation (PD duration, hours of OFF time, hours of dyskinesia, Levodopa equivalent daily dosage).

Details of statistical methods will we presented in a separate statistical analysis plan (SAP). All statistical analyses will be carried out by means of the SAS® package (version 9.4 or higher).

9.8 **Quality Control**

The personnel at each PMOS site may be trained on the protocol and PMOS procedures by a CRA at a site training visit, via telephone or on-site.

Throughout the PMOS, the CRO and AbbVie will periodically follow-up with sites to ensure that SAEs and PCs are being reported.

All PMOS data will be entered into the eCRF which will be accessed via a web-based EDC system. Any necessary corrections will be made to the database and documented via queries, source data clarification form or audit trail. A manual review of elected line listings will also be performed at the end of the PMOS. A clinical monitor working on behalf of AbbVie will perform a final site closure visit when the site or study is closed.

9.9 **Limitations of the Research Methods**

The primary limitation of this PMOS is that it is performed in an open-label, noncontrolled and non-randomized design with mainly retrospective data capturing. Thus, selection and reporting bias cannot be excluded. In order to minimize these biases, all eligible patients shall be enrolled in a consecutive manner.

Moreover, as only patients on current LCIG therapy are included, data of patients who discontinued treatment will not be collected. Therefore, comprehensive safety conclusions may not be drawn from the study results.

Finally as the study aims to identify treatment predictors based on patient's and physician's profiles; however it can be influenced by LCIG country specific prescription or reimbursement status. Therefore, country origin would be taken into account when analyzing treatment predictors.

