#### 6.4 Primary variable

There are two primary variables:

1. LCIG monotherapy 1 (yes, no) at LCIG initiation and at 3, 6, 9, and 12 months after LCIG initiation

with the following definition:

- LCIG monotherapy means that the patient is not on any add-on PD medication or PD therapy at the respective time point.
- 2. LCIG monotherapy 2 (yes, no) at LCIG initiation and at 3, 6, 9, and 12 months after LCIG initiation

with the following definition:

LCIG monotherapy means that the patient is allowed to take an add-on PD medication or PD therapy at the respective time point, however, only in the evening after the LCIG infusion is completed (i.e. reason for start of add-on PD medication: other).

Additional specifications for both variables are:

- Medications for indications secondary to PD are allowed.
- If the reason for add-on PD medication is missing the medication will be considered as taken during LCIG infusion (i.e. no monotherapy).
- LCIG initiation date is the start date of the first LCIG infusion.
- 3 months after LCIG initiation is calculated as LCIG initiation date + rounded (3 [months] x 30.4 [days]). 6, 9, and 12 months after LCIG initiation will be calculated analogously.
- For LCIG initiation date with missing day the 15th will be used.

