#### Reasons:

- For each add-on PD medication/therapy at the time points LCIG initiation and at 3, 6, 9, and 12 months after LCIG initiation and at visit::
  - Reason for start (multiple answers)
  - If not ongoing: reason for discontinuation (multiple answers)
- Reason for change on LCIG dose in general
- Reason for LCIG dose changes (multiple answers) by 5%, 10%, 15%, 20% or 25% or higher
- Reason for substantial LCIG dose changes (multiple answers) with substantial change defined as any increase or decrease of the total daily LCIG dose by more than 20%
- Latency and duration of treatments:
  - For patients with add-on PD medication or PD therapy at LCIG initiation: Time from LCIG initiation until LCIG is given as a monotherapy (separately for monotherapy 1 and monotherapy 2 definition)

[figure not shown]
Only patients with add-on PD medication or PD therapy at LCIG initiation

 For patients with add-on PD medication or PD therapy at LCIG initiation and separately for patients with and without ongoing monotherapy at visit: Duration of LCIG monotherapy (separately for monotherapy 1 and monotherapy 2 definition) Only patients with add-on PD medication or PD therapy at LCIG initiation Analysis a) Without ongoing monotherapy until visit

Analysis b) With ongoing monotherapy until visit

- For each add-on PD medication/therapy:
   Time from LCIG initiation until the respective add-on PD medication/therapy is started or changed
- Time from LCIG initiation until the first LCIG dose change by 5%, 10%, 15%, 20% or 25%
- Time from LCIG initiation until the first substantial LCIG dose change with substantial change defined as any increase or decrease of the total daily LCIG dose by more than 20% in relation to first LCIG infusion
- LCIG monotherapy (1 and 2) vs. LCIG plus add-on PD medication:
  - o HCRU:
    - Primary occupation (retired, on sick leave, unemployed, working full time, working part-time, student)
      - If retired: due to PD (yes, no)
      - If on sick leave: due to PD (yes, no)
      - If unemployed: due to PD (yes, no)
    - Permanent living in a nursing home/institution (yes, no)
    - Help in daily activities
    - Frequency of visits:
      - General practitioner

- Nurse
- Occupational/speech therapist
- Physiotherapist
- Psychologist and/or psychiatrist
- Dietician
- Discussion of LCIG monotherapy (yes, no, patient did not remember)
- Offering of LCIG monotherapy (yes, no, patient did not remember)

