#### 7.4 Patient data

Patient disposition will be evaluated for all patients enrolled.

All other variables will be evaluated for FAS according to the methods described in Section 7.1.

Patient data will be analyzed overall and separately for the following three groups:

- Patients on monotherapy 1 at 12 months after LCIG infusion (see Section 6.4)
- Patients on monotherapy 2 at 12 months after LCIG infusion (see Section 6.4)

Patients not on monotherapy 2 at 12 months after LCIG infusion (see Section 6.4) For duration of 'Off' state (hours) and duration of dyskinesia (hours) the difference will be calculated between the time points 'prior to LCIG initiation' and visit (UPDRS IV: modified items 39 and 32) as value at visit minus value prior to LCIG initiation.

'Other' co-morbidities will be coded using MedDRA. Incidence rates will be calculated with respect to System Organ Class and Preferred Term.

Regarding the 'Historical therapy discontinued prior to considering LCIG initiation' patient based means that a therapy type will only be counted once per patient.

A list of other medications and therapies only for indications secondary to PD will be provided including the following information:

- PatientID
- Name of concomitant medication or therapy
- Indication
- Total daily dose
- Dose unit
- Start date
- End date
- Ongoing at the end of study

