#### 7.6 Secondary variables

The secondary variables will be evaluated for FAS.

Secondary variables will be analyzed overall and separately for the following three groups:

- Patients on monotherapy 1 at 12 months after LCIG infusion (see Section 6.4)
- Patients on monotherapy 2 at 12 months after LCIG infusion (see Section 6.4)
- Patients not on monotherapy 2 at 12 months after LCIG infusion (see Section 6.4)

Regarding 'Add-on PD medication' patient based means that a therapy type will only be counted once per patient. The variables total daily dose, LEDD and posology will additionally be analyzed per category by summing up the values of the corresponding medication/therapy.

Regarding total dose per day the difference will be calculated between the time points LCIG initiation start, 12 months after LCIG initiation start and visit as follows:

- Total dose per day at 12 months after LCIG initiation start minus total dose per day at LCIG initiation start
- Total dose per day at visit minus total dose per day at LCIG initiation start
- Total dose per day at visit minus at 12 months after LCIG initiation start

If applicable, levodopa equivalent daily dose (LEDD) will be calculated separately for each medication/therapy as total daily dose in mg multiplied with the respective factor (from Table 7-1; [1], [2], [3]). Exceptions are entacapone, tolcapone and opicapone: irrespective of the entacapone dose (or tolcapone or opicapone dose, respectively) the corresponding levodopa dose is multiplied by the given factor. This will then be considered as LEDD for entacapone (or tolcapone or opicapone, respectively).

The total daily LEDD will be the sum over all daily LEDDs which were calculated separately for each medication at the respective time point.

Table 7-1: Factor for levodopa equivalent daily dose

Medication	Factor
Levodopa/carbidopa	1.11
Levodopa/benserazide	1
Levodopa/carbidopa/entacapone	1.33
Amantadine	1
Apomorphine	10
Cabergoline	80
Entacapone	concomitant levodopa multiplied by 0.33
Tolcapone	concomitant levodopa multiplied by 0.5
Pramipexole	100
Rasagiline	100
Ropinirole	20
Rotigotine	30
Selegiline oral	10
Opicapone	concomitant levodopa multiplied by 0.65
Safinamide	
Budipine	5

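### Outcomes measured only at the study visit are grouped by monotherapy status at month 12; tables by status at the visit should be added

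*SAP*

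**What the plan says.** SAP 7.6 states: "Secondary variables will be analyzed overall and separately for the following three groups". The three groups are monotherapy 1 at month 12, "Patients on monotherapy 2 at 12 months after LCIG infusion (see Section 6.4", and "Patients not on monotherapy 2 at 12 months after LCIG infusion (see Section 6.4". SAP 7.4 applies the same split to patient data, which include the patient questionnaires and physician scales: "Patient data will be analyzed overall and separately for the following three groups".

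The two definitions are in SAP 6.4. For monotherapy 1, "LCIG monotherapy means that the patient is not on any add-on PD medication or PD therapy at the respective time point". Monotherapy 2 also admits patients whose add-on is taken only in the evening, once the infusion has ended. An add-on with no recorded reason counts as taken during the infusion.

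In SAP Table 4-1, PDQ-8, QUIP-RS, PDSS-2, NMSS, BMQ and HCRU appear only in the patient-visit column. UPDRS and MMSE are taken before LCIG and at the visit. Inclusion criterion 1 sets a minimum of 12 months on LCIG and no maximum.

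SAP 6.5 introduces the HCRU comparison as "LCIG monotherapy (1 and 2) vs. LCIG plus add-on PD medication", without a time point. Protocol 9.7 adds: "Confidence intervals will also be calculated for differences between pre-defined groups of patients, if appropriate", and gives monotherapy versus add-on as its example.

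**The concern.** Treatment status and outcome are taken at different times. Protocol 9.1 describes the visit as cross-sectional, assessing patients as they are now, and the instruments fit that aim. PDSS-2 and UPDRS Part IV cover the past week, PDQ-8 and NMSS the last month, and the specific section of the BMQ asks about medicines currently prescribed. A patient who was on monotherapy at month 12 and later received an add-on would report views on a combination regimen in a column headed monotherapy.

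The gap may be long. Protocol 7.0 says the system has been marketed for over 10 years, so an interval of several years is possible.

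The SAP itself expects change after month 12. It tabulates add-on medication and infusion settings between month 12 and the visit, computes the dose difference over that period, and separates monotherapy that is ongoing at the visit from monotherapy that is not. What is at stake is whether the study can describe current monotherapy patients against current add-on patients. The primary percentages are not affected.

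**Working it through.** **1. The plan's own figure.** The only sample-size calculation (Protocol 9.5) uses a two-sided 95% interval, p = 0.50 and a half-width of 0.05. Then n = 1.96² × 0.50 × 0.50 / 0.05² = 384.15, rounded up to 385, which reproduces the stated figure. It concerns a single percentage and does not cover group comparisons.

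**2. Can status at the visit be derived?** Yes. SAP 6.5 tabulates each add-on at the visit, and also the reason for starting it, which is what separates monotherapy 2 from other add-on use. The SAP already uses ongoing monotherapy at the visit, but only in the duration analysis and only for patients with an add-on at LCIG initiation.

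**3. Effect of switching.** Let M and A be the mean outcomes of patients on monotherapy and on add-on at the visit. Let a be the share of the month-12 monotherapy group that moved to add-on by the visit, and b the share of the month-12 add-on group that moved to monotherapy. Assume that, given visit status, the outcome does not depend on month-12 status.

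- Month-12 monotherapy group: (1 - a)M + aA
- Month-12 add-on group: bM + (1 - b)A
- Difference: (1 - a - b)(M - A)

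**4. Illustration.** The switch rates and effect size are assumptions, because the documents give neither. I take N = 400 and a standardised difference of 0.30 by visit status. The share on monotherapy 2 at month 12 is set at 40%, the upper end of the registry range of 36-40% in Protocol 7.0. Power is two-sided at 5%, by normal approximation with SD 1 in every group.

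| a | b | Difference kept | Power, month-12 groups | Power, visit groups |
|---|---|---|---|---|
| 0% | 0% | 100% | 84% | 84% |
| 5% | 5% | 90% | 75% | 84% |
| 10% | 10% | 80% | 65% | 84% |
| 20% | 10% | 70% | 54% | 83% |
| 20% | 20% | 60% | 42% | 85% |

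For a = b = 10%, the month-12 groups have 160 and 240 patients, so SE = √(1/160 + 1/240) = 0.102. The retained difference is 0.80 × 0.30 = 0.24, z = 0.24/0.102 = 2.35, and power = Φ(2.35 - 1.96) = 65%. With 77% on monotherapy at month 12 (the open-label trial figure in Protocol 7.0) and a = b = 10%, power is 52% against 77%.

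**5. Overlap of the three groups.** SAP 6.4 allows three kinds of patient:

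| Patient at month 12 | Monotherapy 1 | Monotherapy 2 | Not monotherapy 2 |
|---|---|---|---|
| No add-on | yes | yes | no |
| Evening-only add-on | no | yes | no |
| Other add-on, or reason missing | no | no | yes |

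The third column is the exact complement of the second and shares no patient with the first. Only monotherapy 1 and monotherapy 2 overlap. If f is the share of the monotherapy 2 group that also meets monotherapy 1, the monotherapy 1 versus monotherapy 2 difference is (1 - f) times the contrast between no-add-on and evening-only patients: 50% of it at f = 0.5, 20% at f = 0.8.

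**6. Intervals.** SAP 7.1 plans confidence intervals for proportions. Neither 7.4 nor 7.6 adds one for a difference between groups, and the change from Protocol 9.7 is not explained, although SAP 2.5 says substantial deviations are described.

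**The case against.** The month-12 grouping has real merits. It fixes status no later than the visit outcome, matches the last primary time point (SAP 6.4) and is the response in the regressions (SAP 7.8). Grouping by visit status sets outcomes against treatment that may have been chosen because of them, which is confounding by indication. Some HCRU items look back: problems before LCIG, who influenced the decision to start, and whether monotherapy was discussed or offered. Visit status is not clearly right for these. All this stands, and it argues for adding a grouping rather than replacing one.

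The SAP also follows the primary variable between month 12 and the visit (7.5), reports monotherapy duration, and allows extensions (7.10). These would reveal changes in status, but they do not regroup any outcome, and 7.10 commits to no particular table.

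A reader might infer from the nested definitions that overlap itself dilutes the monotherapy versus add-on comparison, or rules out the interval foreseen in Protocol 9.7. The documents do not support this. Monotherapy 1 versus not monotherapy 2, and monotherapy 2 versus not monotherapy 2, are contrasts between disjoint groups and can carry ordinary intervals. The missing intervals are a separate omission, and the protocol promised them only where appropriate. Counting evening-only users as monotherapy also fits the definition in Protocol 9.2.7.7, which concerns infusion hours. Their counts and means can be recovered by subtracting columns, and so can those of the complement of monotherapy 1; quantiles cannot. This part of the point is about readability.

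**Conclusion.** The point holds for outcomes that describe the patient at the visit: PDQ-8, NMSS, PDSS-2, QUIP-RS, BMQ, current-status HCRU items, and the visit values of UPDRS and MMSE. The SAP labels these by a status that may be out of date, and plans no table by current status although the data allow one.

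Each 10 percentage points of combined switching (a + b) removes 10% of the visit-status difference, provided switching is unrelated to outcome given visit status. The actual size is unknown, because neither a switch rate nor the distribution of time to visit is given; it is zero if nobody switches. A reader might infer that the bias always runs toward zero. That does not follow: if patients who worsen are the ones who receive an add-on after month 12, it can run either way.

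The matter is moderate in weight. It affects how the secondary, descriptive comparisons are read.

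**What to change.** In SAP 7.4 and 7.6:

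- For the current-status visit outcomes listed above, add tables by monotherapy status at the visit, derived for all patients by the SAP 6.4 rules. Keep the month-12 tables alongside.
- Keep month-12 grouping for variables up to month 12 and for look-back HCRU items. Assign HCRU items one by one, since the documents do not state a recall window for each.
- Report the cross-table of month-12 by visit status, and the distribution of time from LCIG start to visit. These replace the assumed a and b with observed values.
- Show three disjoint groups: no add-on, evening-only add-on, other add-on. Evening-only patients, and the two groups that make up the complement of monotherapy 1, can then be read directly.
- Give 95% confidence intervals for differences between monotherapy and add-on groups, as Protocol 9.7 foresees, or state why they are not appropriate.

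The cost is SAP wording and a second set of clearly labelled tables; no new data are needed. The visit-status comparisons should be presented as descriptive, with a note that they are open to confounding by indication.

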To assess the generalizability of the data from the patients enrolled, the physician will be asked to document on a separate Case Reporting Form the number of patients who are eligible but refuse to participate in the study. Only age ranges (<30 years, 30-45 years, 45-65 and > 65 years) and reason(s) for not participating will be collected.

The primary endpoint of this PMOS will be the percentages of APD patients on LCIG monotherapy right after LCIG initiation and at 3, 6, 9, and 12, respectively.

The secondary endpoints are:

- Descriptive data from patient's PD medication:
 - For add-on PD medication: percentage of patient on each PD medication (by drugs and class), total daily dose and levodopa equivalent Daily dose (LEDD), posology (number of times per day);
 - For LCIG infusion settings and substantial dose adjustments: total dose per day and specific for each type of dose (morning dose and continuous dose) and number of hours of infusion.

- Tapering process: number of days required for the tapering process, total dose per day and posology for add-on PD medication prior to LCIG initiation, at LCIG initiation (titration) or during ongoing LCIG treatment
- Main reasons for introduction or tapering of add-on PD medication or LCIG substantial dose adjustments
- Latency and duration of treatments data:
 - Number of days or months from LCIG initiation until LCIG is given as a monotherapy and the duration of LCIG monotherapy.
 - Number of days or months from LCIG initiation until the introduction or tapering of each PD medication, or until any LCIG substantial dose adjustments.
- LCIG monotherapy vs LCIG plus add-on PD medication data:
 - Healthcare Resource Utilization, as measured by Healthcare Resource Utilization Questionnaire (HCRU)
 - Patient's, caregiver's, and physician's overall preference on LCIG monotherapy vs. LCIG plus add-on PD medication, percentage of patient's and physician's preference for each of the options
 - Predictors for LCIG as monotherapy vs. LCIG plus add-on PD medication based on the patient's profile, including socio-demographics, clinical status (motor and non-motor symptoms), Levodopa-equivalent dose (LED), PD medication and Quality of Life
 - Predictors for LCIG as monotherapy vs. LCIG plus add-on PD medications based on the physician's profile including experience as measured by number of years on APD patient management, number of years using LCIG therapy, and number of patients on LCIG therapy

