#### 6.5 Secondary variables

#### Descriptive data from patient's PD medication

Add-on PD medication:

At the time points LCIG initiation and at 3, 6, 9, and 12 months after LCIG initiation, at visit and at appropriate time points between 12 months after LCIG initiation and the visit:

 Add-on PD medication (multiple answers; category and medication/therapy; patient based)

Category and medication/therapy are as follows:

Category	Medication/therapy
Levodopa	Levodopa/carbidopa Levodopa/benserazide Levodopa/carbidopa/entacapone Other
COMT inhibitor	Entacapone Tolcapone Opicapone Other
Dopamine Agonist (excluding Apomorphine)	Pramipexole Ropinirole Cabergoline Rotigotine Other
MAO Inhibitor	Selegiline Safinamide Rasagiline Other
NMDA Antagonist	Budipine Amantadine Other
Apomorphine	Apomorphine intermittent injection SC Apomorphine subcutaneous continuous infusion 30mg/ml solution Other
Anticholinergics	Anticholinergics Other

Surgical therapy	Pallidotomy Thalamotomy Deep brain stimulation (DBS) Stem Cell Transplant Other
Other	-

- Total daily dose separately for each category and for each medication/therapy (except all 'Other', Anticholinergics, and Surgical therapy; Apomorphine only if possible)
- Levodopa equivalent daily dose (LEDD) separately for each category and for each medication/therapy if applicable (see Section 7.6)
- Total daily LEDD (in mg; see Section 7.6)
- Posology (i.e. average number of intakes per day) separately for each category and for each medication/therapy (except all 'Other' and Surgical therapy)
- Add-on PD medication in categories and medication/therapy (multiple answers)

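### The SAP's per-category total daily dose adds raw milligrams, which its own LEDD factors show are not equipotent for dopamine agonists, MAO inhibitors and NMDA antagonists

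*SAP*

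**What the plan says.** SAP 6.5, under add-on PD medication, lists as a secondary variable "Total daily dose separately for each category and for each medication/therapy (except all 'Other', Anticholinergics, and Surgical therapy; Apomorphine only if possible". SAP 7.6 gives the rule for the category level: "The variables total daily dose, LEDD and posology will additionally be analyzed per category by summing up the values of the corresponding medication/therapy".

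The dose summed is in plain milligrams. The potency factor is applied only to obtain LEDD, which 7.6 says is "calculated separately for each medication/therapy as total daily dose in mg multiplied with the respective factor". SAP 6.5 also plans "Levodopa equivalent daily dose (LEDD) separately for each category and for each medication/therapy if applicable", so a potency-adjusted class measure stands beside the raw one.

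The dopamine agonist category in 6.5 comprises "Pramipexole Ropinirole Cabergoline Rotigotine Other". The MAO inhibitor category holds selegiline, safinamide and rasagiline, the NMDA antagonist category budipine and amantadine, and the COMT inhibitor category entacapone, tolcapone and opicapone. Entries classed as Other do not contribute to total daily dose.

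The variables are summarised at LCIG initiation, at 3, 6, 9 and 12 months, at the visit and at points between, overall and in three groups defined by monotherapy status at 12 months.

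Protocol 9.1 words the endpoint as "percentage of patient on each PD medication (by drugs and class), total daily dose and levodopa equivalent Daily dose (LEDD"). There, the reference to drugs and class qualifies the percentage of patients. It does not clearly ask for a milligram dose per class.

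**The concern.** A sum or mean of milligrams over different drugs can be read as a dose only if a milligram of each does about the same. The SAP's own conversion table says that in three categories it does not. The class figure then depends on which drugs the patients happen to take as well as on how intensively they are treated. This needs no patient on two agents at once: averaging over patients who take different agents is enough.

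Describing PD medication management is the first secondary objective, and it is repeated for each country with at least 20 patients. If groups or time points differ in drug mix, the raw class dose will differ even where dopaminergic load is the same. The report would then carry two class-level dose measures that could point in opposite directions. SAP 2.5 makes the SAP's methods binding on programming, so the tables would be produced as written.

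**Working it through.** The plan states no numerical result for class-level dose, so there is no figure to reproduce. The check uses the SAP's own "Table 7-1: Factor for levodopa equivalent daily dose" and the category lists in 6.5.

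**Step 1: spread of potency per milligram within a class** (largest factor ÷ smallest factor)

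| Category | Factors in Table 7-1 | Spread |
|---|---|---|
| Dopamine agonists | pramipexole 100, cabergoline 80, rotigotine 30, ropinirole 20 | 100/20 = 5-fold |
| MAO inhibitors | rasagiline 100, oral selegiline 10, safinamide blank | 100/10 = 10-fold |
| NMDA antagonists | budipine 5, amantadine 1 | 5/1 = 5-fold |
| Levodopa products | with carbidopa and entacapone 1.33, with carbidopa 1.11, with benserazide 1 | 1.33/1 = 1.33-fold |
| COMT inhibitors | no factor per mg of the drug itself; LEDD is a multiple of the accompanying levodopa | not defined |

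**Step 2: milligrams that give one and the same LEDD** (mg = LEDD ÷ factor). The LEDD values are chosen for arithmetic only and are not dosing statements.

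- Dopamine agonists, LEDD 300 mg: 300/100 = 3 mg pramipexole; 300/80 = 3.75 mg cabergoline; 300/30 = 10 mg rotigotine; 300/20 = 15 mg ropinirole.
- MAO inhibitors, LEDD 100 mg: 100/100 = 1 mg rasagiline; 100/10 = 10 mg selegiline.
- NMDA antagonists, LEDD 100 mg: 100/5 = 20 mg budipine; 100/1 = 100 mg amantadine.
- Levodopa products, LEDD 300 mg: 300/1.33 = 226 mg to 300/1 = 300 mg.

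**Step 3: effect of drug mix on a group mean.** Let every patient in a group have a dopamine-agonist LEDD of 300 mg, with a share *s* on ropinirole and the rest on pramipexole. The raw class mean is 15*s* + 3(1 − *s*) mg.

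| Share on ropinirole | Raw class mean | Class LEDD mean |
|---|---|---|
| 0% | 3 mg | 300 mg |
| 50% | 9 mg | 300 mg |
| 100% | 15 mg | 300 mg |

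**Step 4: can the two measures disagree in direction?** Take one group all on 3 mg pramipexole and another all on 12 mg ropinirole. The raw class dose is 12/3 = 4 times as high in the second group. The LEDD is 3 × 100 = 300 mg in the first and 12 × 20 = 240 mg in the second, which is 20% lower. They can.

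**Step 5: where the arithmetic stops.** For levodopa products the sum still roughly tracks intensity. For COMT inhibitors 7.6 computes LEDD without regard to the drug's own dose, so Table 7-1 cannot show how far apart their milligrams lie and gives no basis for adding them. Apomorphine has a single factor (10), so the point does not reach it.

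**The case against.** The strongest reply is that this is a redundant descriptive table and that the sound version is already planned. It is largely right about reach. The sentence in 7.6 that sums milligrams also sums LEDD, and 6.5 plans dose and LEDD for each drug. The primary endpoint is monotherapy yes or no, the regressions in 7.8 use total daily LEDD, and the SAP specifies no test on class milligrams.

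A reader might infer several stronger things that the documents do not support:

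- *A switch within a class will be reported as a large dose change*, for example an 80% fall from 15 mg to 3 mg. No within-patient change in class dose is planned for add-on drugs. The differences listed in 7.6 appear to concern the LCIG dose, since 6.5 uses the same term for the LCIG total in ml. Tapering and latency are specified for each add-on drug. Only the cross-sectional summaries are exposed.
- *All three monotherapy groups will be distorted at 12 months.* By definition, patients on monotherapy 1 at that point take no add-on medication, so they have no mix to distort.
- *The distortion is known to be common.* Protocol section 7 cites 30% dopamine agonist use on LCIG in an Italian observational study. That is use of any agonist and says nothing about which ones. The documents give no data on drug mix.
- *Every drug class is affected alike.* Levodopa products are not materially affected, and Table 7-1 is silent on COMT inhibitor milligrams.

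Reporting LEDD alone at class level would also go too far. It would drop class-level posology for no reason and leave safinamide unresolved. What survives is narrower: in three categories the raw sum is still planned, adds nothing that LEDD and the per-drug doses do not, and can contradict the class LEDD.

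**Conclusion.** The concern holds for the per-category milligram total daily dose in dopamine agonists, MAO inhibitors and NMDA antagonists. At equal LEDD, drug mix alone can move the class figure up to 5-fold, 10-fold and 5-fold respectively. These are limits set by the factors in Table 7-1, taken at face value; the MAO figure leaves out safinamide. The distortion actually seen will depend on how drug mix differs between groups and time points, which the documents do not tell us. For COMT inhibitors the sum is uncalibrated rather than shown to be wrong. For levodopa products the spread is at most 1.33-fold and the sum is roughly interpretable, assuming the recorded dose of combination products is the levodopa component.

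This is a presentation fault in a descriptive secondary variable. It does not undermine the class-level LEDD, the primary endpoint or the regressions. It is worth correcting because the change is small and avoids publishing two class-level measures that can conflict.

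**What to change.** Amend the wording in two places.

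- **SAP 6.5:** limit total daily dose in milligrams to individual medications. The levodopa category sum may stay, and so may apomorphine, which is one substance with one factor.
- **SAP 7.6:** remove total daily dose from the per-category summing rule, with the same exceptions. Name the already planned LEDD as the class-level dose measure. Keep category-level posology and the percentage of patients on each category.

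Two clarifications belong with this. State how safinamide, whose factor is blank in Table 7-1 as available to us, enters the MAO-inhibitor class LEDD: with a stated factor, or excluded with the number of patients affected reported. Add a table note that the COMT inhibitor LEDD is a multiple of the accompanying levodopa and does not measure the COMT inhibitor's own dose.

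The cost is a SAP wording change and the loss of a few descriptive class-level milligram tables. Per-drug doses remain, no extra data are needed, and the protocol endpoint in 9.1 is still met.
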